2. Estimate the degree to which expressive nonverbal capacity predicts the social self-management trajectory. Hypothesis: People with PD with higher expressive capacity at baseline will have more positive social trajectories over time than people with less expressive capacity.
3. Determine the moderating effect of gender on the association between expressive capacity in PD and change in social self-management. Hypothesis: Gender will moderate the association. The social trajectories of women are expected to be more vulnerable to the influence of expressive disability than the trajectories of men.

Methods/design

Research design

This prospective cohort study design tracks general patterns of the sample as a whole as well as variation among individual trajectories in social self-management. The tracking creates evidence necessary to develop social life interventions that address the typical issues faced by people living with the disease as well as individual variations in needs. Over a 3-year period, the study plans to follow 120 individuals with PD and their

associated primary care partner. Individuals with PD are included whether or not they have an identified care partner.

There are seven full assessments of approximately two hours duration and in-person, one at baseline and one every six months thereafter, with six in a clinical research lab and one in the home. Between the 6-month full assessments, there is an additional brief telephone call (15 to 30 minutes), totaling seven phone calls over three years. This innovative design of 14 assessments over the three years aims at detecting social or health triggers that affect individual participant's trajectories [4]. Frequent points of contact, while also building statistical power, increases the possibility of capturing remembered details of daily life that send health patterns into non-linear trajectories, such as anniversaries, retirement, bad colds or significant family events [5,6].

Ethics review

Recruitment, consent and data collection protocol have been approved by Social, Behavioral & Educational Institutional Review Board of Tufts University Medford Campus (protocol # 1212038), and the Boston University Medical Campus (BUMC) Institutional Review Board (protocol # H-32114).

Participants

Recruitment

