Each of the seven in-person assessment sessions is designed to take a maximum of two hours to complete. At each session, initially, participants with PD and care partners are interviewed separately with parallel questionnaires to assess each of their daily life activities, health and quality of life. After separate interviews, the two are interviewed together about their combined social self-management. Participants with PD are asked to take their medication approximately 45 minutes before their assessment session in order to be “on,” that is, moving and functioning at maximal capacity during their session. Upon arrival they are asked about the timing and effectiveness of their medication on that day as well as the severity of their movement symptoms. Updates on medication changes and background information are collected, such as: marital status, living arrangement, occupational status, and notable mental and physical health or life events in the recent past or since the previous visit.

Covariate measures

The diminished expressive capacity that occurs in PD is a motor problem that can be confounded with the motor symptoms of depression, apathy or cognitive impairment [8,9]. At initial screening for this study, individuals with dementia are screened from

participation (i.e., ≥ 26 on the MMSE) yet dementia may develop over the course of the study. Participants are monitored for dementia and basic cognitive functioning at every visit with the Montreal Cognitive Assessment [10]. The Geriatric Depression Scale [11] is administered to participants at every visit to monitor depression throughout the study period. These measures are used for covariate analysis and to group individuals for blocked analyses.

Primary interview measures

Unless noted as otherwise, assessments are administered to both the participant with PD and the care partner. Variables and assessment procedures are described below in order of priority to the study.

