bodily discomfort. A higher score indicates a higher self-perceived frequency of quality of life and health problems in the past month that are due to the disease, with 0 indicating *never a problem* and 100 *always a problem*. The index and domain scores have adequate internal consistency, convergent validity with health status and quality of life measures, test-retest reliability, and responsiveness to intervention. The exception is the social support scale which has weak psychometric properties [34]. The PDQ-8 summary index is a short form of the PDQ-39 that is administered in place of the PDQ-39 for approximately half of the in-person assessments to allow for time to administer the MDS-UPDRS once per year. The PDQ-8 provides adequate psychometrics for detecting minimally important differences in change in health status of PD over a 1-year period [32].

- The MDS-UPDRS is a widely-used clinical assessment and research tool for assessing motor and non-motor symptom severity [33]. Parts I and II assess self-reported non-motor and motor aspects of daily living. Parts III and IV assess observed motor capacity and extent of abnormal movement and are the primary measures for this project. This assessment is administered once per year.

Brief telephone assessments

Calls are scheduled to interview the participant with PD and the care partner separately. The primary objective of these calls is to help inform findings relative to shifts in social trajectories. Participants have the opportunity to elect an alternate means of assessment, such as a mailed questionnaire, if a telephone assessment is perceived as burdensome. It has been found that telephone assessments that occur between

scheduled in-clinic visits are welcomed by people with PD [35], who typically do not find them burdensome, and experience them as comforting, positive attention. The 15- to 30-min audiotaped protocol involves the following assessments:

1. Recent important life events, changes in physical and mental health, and medication changes since the previous assessment,
2. PDQ-8 (administered only to the participant with PD),
3. Social Isolation domain-NHP,

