4. Three simple 5-point scale questions (1= low, 5 = high), followed by open ended probes: 1) *How satisfying is your social life right now?* (probes: stressful or exciting changes in networks, finances, activities); 2) *How satisfied are you with managing the effects of PD on your life right now?* (probes: physical, social, emotional effects); and 3) *How satisfied are you with your health right now?* (probes: physical, social, emotional health), and
5. SF-12 (version 2).

Measure of expressive nonverbal capacity

The Interpersonal Communication Rating Protocol: Individual Expressive Behavior (Parkinson's Disease Version) (ICRP-IEB) [36] is used as the primary measure of the expressive capacity of participants with PD in videotaped discussions about management of social activities at baseline and 6-month follow-ups. This rating protocol employs a "thin slice" method, which links discrete behaviors (e.g., an upturned lip, a movement of the limb) into socially meaningful units (e.g., smiling, happiness, dominance) that are closely aligned with individuals' social life outcomes (e.g. health or work success) [37-39]. The primary method is to extract short segments (thin slices)

from a video or audiotaped social interaction, and have raters draw behavioral or social conclusions from the segments. For this project, 60-second clips are extracted from the videotapes at two standardized time points during the interview: first when the participant is asked to describe a frustrating activity, and again when asked to describe an enjoyable activity [40]. Sixty-second clips have been found to yield optimal accuracy-to-slice length ratio for making judgments of behavior [41]. Using the methods described in the ICRP-IEB manual, trained research assistants view the clips separately and rate the quality, intensity and frequency of expressive behavior on 20 discrete actions (e.g., smiling, gesturing, bodily movement, vocal tone) and PD symptoms (tremors and postural slouch) that observers use as cues to form judgments about a target individual's emotions, thoughts, social motives and personality. Previous studies provide evidence that expressive capacity in PD can be measured reliably and validly at this social level of analysis [40,42]. Expressive behavior composite scores are formed based on principal component analyses.

Power Calculation

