social isolation score, 6) positive interaction with partner score, 7) felt stigma and enacted stigma scores (SSCI), 8) physical and mental health scores (SF-12), 9) health quality of life with PD scores (PDQ-39 or PDQ-8), and 10) motor capacity scores (MDS-UPDRS, Parts III and IV). Outcomes measured at all 14 time points are: 1) physical and mental health scores (SF-12), 2) health quality of life with PD score (PDQ-8), and 3) loneliness score (Social Isolation, NHP). Temporal dynamics of these outcomes will be explored in order to better understand the similarities, differences and factors governing such dynamics. By including random effects, the population trajectory and the degree of variations of individual trajectories will be explored. Outcomes reported by both the person with PD and the care partner will depict both perspectives, which enable an assessment of the synchronicity between the two sources. Statistical tests of interaction terms will evaluate whether particular factors affect the ratings of one source more than another.

The multilevel models can accommodate subjects with and without care partners, as well as incomplete data collection, as long as data are missing at random [49]. For sensitivity analyses pattern mixture models are used to account for the possibility of informative missingness. The models will stratify by pattern of and reason for missing data [50].

Effects of triggers on trajectories: Exploratory analysis

For exploratory purposes, the general multilevel modeling approach is expanded to consider potential effects of unanticipated triggers assessed at the individually identified time points [4]. The timing of measurements will be calibrated as “time elapsed since an event” or “time preceding an event”. Recalibration enables synchronization of triggering

events across the cohort, allowing determination of synchronized changes in one of the outcomes of interest after occurrence of an unanticipated event. For example, there may be an increase in loneliness following hospitalization of a spouse or a decline in social activity following an episode of physical illness.

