Non-linearities with non-parametric fitting will be explored if a sufficient number of subjects have experienced a similar event. For example, some social triggers may have a temporary U-shaped trajectory. This description of potential rapid or unexpected changes in the trajectories is highly innovative for research in the social aspects of PD and other chronic degenerative conditions. Adding trigger event monitoring to the research design builds power for repeated measures, and it may illuminate the understanding of disease progression as a social ecological phenomenon.

Aim 2: Expressive nonverbal capacity as predictor

Analysis will start with a simple linear model, considering a random intercept and slope for each individual. The assumption is that, the variation among individuals in the intercept and slope of their trajectories can be explained by subject characteristics, including expressive capacity at baseline. For example, it may be found that the rate of change in the study outcomes may vary and depends on expressive capacity at baseline. This preliminary step will guide the further model building.

Multivariate models are built by first adding demographic factors, then clinical factors, and then other variables of interest including masking, life stage, and access to support. The number of variables are reduced in each group before adding the group to the model, and the number of variables are reduced further as groups are added. Since expressive masking will be measured at follow-up times as well, repeated measures

analyses are performed to estimate the relation between change in expressive masking and change in social self-management.

Aim 3: Moderating effect of gender

Models developed for Aim 1 and 2 are applied to explore in detail the effect of gender on the modeling results. For example, it may be found that rates of change in the study outcomes depend on both, expressive capacity at baseline and gender. The test of the moderating effect of gender on the relationship between expressive masking and social self-management in PD is conducted by stratifying the analysis and by including an interaction term between gender and potential predictors. For all models, non-linearities in predictors are tested, and variables are transformed when necessary to obtain good model fit. Models will be examined with respects to over-fitting and fine-tuned to improve their performance.

Problems and Alternative Strategies

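### The exploratory trigger analysis aligns trajectories on events recalled in the same contact that scores the outcome, so state-dependent recall alone can produce the temporary worsening it looks for

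*Combined protocol and SAP*

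**What the plan says.** Everything here is in the combined protocol and SAP.

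- **Where events come from at visits.** Under the in-person assessment procedures, participants update the staff on marital status, living arrangement, occupational status and "notable mental and physical health or life events in the recent past or since the previous visit".
- **Where events come from on calls.** Under Brief telephone assessments, item 1 is "Recent important life events, changes in physical and mental health, and medication changes since the previous assessment". PDQ-8, Social Isolation and SF-12 follow in the same call.
- **Why contacts are frequent.** Research design says that frequent contact "increases the possibility of capturing remembered details of daily life that send health patterns into non-linear trajectories".
- **How events are used.** Under Effects of triggers on trajectories: Exploratory analysis, the multilevel models are extended to "consider potential effects of unanticipated triggers assessed at the individually identified time points". There, "The timing of measurements will be calibrated as" time since or before an event, "allowing determination of synchronized changes in one of the outcomes of interest after occurrence of an unanticipated event". The plan adds that "some social triggers may have a temporary U-shaped trajectory", with non-parametric fitting if enough people had a similar event.

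SF-12, PDQ-8 and Social Isolation are the three outcomes listed for all 14 time points. The section gives no list of event types, no dating rule, no blinding of event coding to scores and no handling of recall that depends on current state. It states no null hypothesis, test or error rate.

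**The concern.** An event enters the analysis only if the participant recalls it and thinks it worth mentioning. Someone who feels worse on the day may be readier to name one. Contacts flagged as events are then selected for bad residuals. Aligning on them shows a worsening at the event and a return towards the person's own level afterwards, even if events do nothing. On PDQ and loneliness, where higher is worse, the artefact is a rise and not a dip.

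A random intercept removes a person's stable level but not this contact-to-contact selection. More participants or contacts would make the artefact more significant, not smaller. Detecting triggers is the stated aim of the 14-assessment design, so ordinary fluctuation could be reported as the effect of life events.

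**Working it through.** The plan gives no figure for this analysis to reproduce. The check asks what a nominal 5% two-sided test does when events have no effect.

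**Inputs from the plan (Power Calculation; Research design):** 120 participants, 14 contacts over three years, dropout 15% per year, ICC 0.82, alpha 0.05. Within-person variance is 1 − 0.82 = 0.18, so the within-person SD is √0.18 = 0.424 outcome SD.

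**Assumptions not in the plan:** an event is named at a contact with base probability p = 0.08. The odds of naming one multiply by OR for each within-person SD of worse score. Each person is aligned on the first named event, which gives about 65 to 70 people.

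**Closed form.** For a normal residual z and a logistic reporting model, the mean of z at flagged contacts is about ln(OR) × (1 − p).

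- Spurious shift ≈ ln(OR) × 0.92 × 0.424. For OR 1.5: 0.405 × 0.92 × 0.424 = 0.158 SD.
- Standard error ≈ 0.424 / √n. For n = 67.5: 0.052.
- Rejection ≈ Φ(shift/SE − 1.96), plus a negligible lower tail. For OR 1.5: 0.158/0.0516 = 3.07, and Φ(1.11) ≈ 0.87.

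**Simulation** (400 runs per cell, no event effect, own intercept and study-time slope removed, uncorrelated residuals):

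| OR | Shift, formula | Shift, simulated | Rejection, formula | Rejection, simulated |
|---|---|---|---|---|
| 1.0 | 0 | 0.00 | 5% | 6% |
| 1.25 | 0.087 | 0.09 | 39% | 36% |
| 1.5 | 0.158 | 0.16 | 87% | 84% |
| 2.0 | 0.271 | 0.27 | 100% | 100% |

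Repeat runs gave 34% to 36% at OR 1.25 and 80% to 84% at OR 1.5.

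**Second set-up** (1,500 runs per cell; random-intercept GLS with linear time, event-time indicators and person-clustered standard errors; p about 0.10). Rejection at the reporting contact was 4.7% at OR 1.0, 40.3% at OR 1.28 and 93.3% at OR 1.65. At OR 1.65 the shifts at the contact before, the reporting contact and the next contact were:

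- uncorrelated residuals: 0.000, −0.203, −0.020 (a one-contact dip and return);
- residual autocorrelation 0.5: −0.087, −0.199, −0.118 (a U-shape).

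**What shrinks it:**

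- *Factual events reported whatever the person's state.* With half the events factual, rejection is 15.9% at OR 1.28 and 43.7% at OR 1.65. With 80% factual it is 6.3% and 11.1%. At OR 1.5 with 80% factual it is about 11%; the formula gives a shift of 0.2 × 0.158 = 0.032 SD and about 9%. With all events factual it is 4.7% to 6.0%.
- *Few people sharing an event type.* With 15 people the standard error is 0.424/√15 = 0.110. Simulated rejection is 10% at OR 1.25 and 26% to 34% at OR 1.5 (formula 12% and 30%). The shift in SD is unchanged.
- *Recall that depends only on a person's stable level.* Rejection is 6.7% to 12.2%, because the random intercept absorbs most of it.

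**Is the next contact clean?** With uncorrelated residuals, nearly so: 5.9% to 11.1% for OR 1.28 to 2.72. With autocorrelation 0.5 left unmodelled, rejection there is 13.3%, 38.3% and 89.3% at OR 1.28, 1.65 and 2.72. With first-order autocorrelation of 0.3 or 0.5 correctly modelled, it is still about 9% to 15% at OR 1.5 and 18% to 21% at OR 2.

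**The case against.** **The analysis is exploratory.** Its heading and opening say so, and it promises description. This stands, and it limits the consequence. It does not remove a directional bias that mimics the expected pattern.

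**Some events are facts.** The plan's own example, hospitalisation of a spouse, can be dated. Visits already record marital, living and occupational changes, and care partners are interviewed separately. This stands: such events carry little of the artefact, and they are the basis of the fix. The plan does not restrict the analysis to them or say that the care partner's account will be used as a check.

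**The U-shape fit needs a similar event in enough people, so pooling every first event overstates the rejection rate.** This stands for the rate (26% to 34% with 15 people at OR 1.5) but not for the size of the bias.

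**Time is measured from the event, not from the report.** True, but contacts are roughly three months apart. For an event since the previous contact, the first score after it is the one taken at the reporting contact.

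**The outcome may not be scored in that contact.** This stands for measures scored only in person, such as the ACS. An event reported by phone distorts those only through autocorrelation.

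**A reader might infer that event times come from the satisfaction questions,** whose prompts include "probes: stressful or exciting changes in networks, finances, activities". The plan does not say this. Events have their own item, listed first in the call.

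**Conclusion.** The concern holds as a gap in an exploratory analysis. Event ascertainment is not separated from the participant's state at the contact that scores the outcome, and a temporary worsening can therefore appear with no event effect.

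For an assumed OR of 1.25 to 2, the spurious shift is about 0.1 to 0.3 SD, and rejection is about 36% to 100% if every event is state-dependent. At OR 1.5, about 80% falls to about 11% when 80% of events are factual, and to about 26% to 34% when 15 people share an event type. The ORs, event frequency and share of factual events are assumptions, so these figures show a range and do not estimate this study's error rate.

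Two stronger readings are not supported. A reader might infer that the analysis tests a different null from the one the plan states, but the plan states none here, and its alpha belongs to a power paragraph that does not mention triggers. A reader might also infer that moving to the next contact cures the problem. It does not when residuals are autocorrelated, and making it the main estimate would demote the short-lived effects the plan wants to describe.

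**What to change.** In the trigger section of the SAP:

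1. Prespecify a trigger analysis limited to datable event types, for example hospitalisation, bereavement, retirement and moving home. Take them from the event-update item and from the marital, living-arrangement and occupational updates already collected, and check them against the separate care-partner interview where there is one. Report other recalled events separately, as descriptive.
2. Have events classified and dated by someone who does not see the outcome scores.
3. Keep study time and serially correlated residuals in the model. Show the pre-event contact as a negative control. A shift there is a warning, but its absence does not clear the result: with uncorrelated residuals that contact rejected only 4.5% to 5.9% of the time while the artefact was present.
4. Add a sensitivity analysis that excludes the reporting contact, and state that it reduces but does not remove the bias when residuals are autocorrelated. Label estimates at the reporting contact as open to state-dependent recall.

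**Cost:** SAP wording, recoding of information already collected and a little more analysis, with no new visits. The downside is fewer usable events. Excluding the reporting contact also misses effects that fade within about three months, which is why it is a sensitivity analysis and not the main estimate.

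### The Aim 2 model is left to an unspecified variable-reduction step that protects neither the exposure nor its admitted confounders, so ordinary p-values and confidence intervals after it cannot be relied on

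*Combined protocol and SAP*

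**What the plan says.** The specific aims state the Aim 2 hypothesis with a direction: "People with PD with higher expressive capacity at baseline will have more positive social trajectories over time than people with less expressive capacity". The Power Calculation section attaches a type I error of 0.05 and 80% power for a correlation of 0.23, so formal inference is intended.

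The Aim 2 analysis section proceeds in two stages.

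- **Preliminary model.** "Analysis will start with a simple linear model, considering a random intercept and slope for each individual". Variation in intercepts and slopes is assumed to be something that "can be explained by subject characteristics, including expressive capacity at baseline". The role of this stage is then limited: "This preliminary step will guide the further model building".
- **Multivariate build.** Demographic factors go in first, then clinical factors, "and then other variables of interest including masking, life stage, and access to support". The reduction rule is "The number of variables are reduced in each group before adding the group to the model", followed by further reduction as groups accumulate.

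The Aim 3 section adds, for all models, transformation of variables to improve fit, and then: "Models will be examined with respects to over-fitting and fine-tuned to improve their performance". It also applies the Aim 1 and Aim 2 models to the gender question.

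The Covariate measures section says that reduced expressive capacity "can be confounded with the motor symptoms of depression, apathy or cognitive impairment". It assigns the Montreal Cognitive Assessment (MoCA) and the Geriatric Depression Scale (GDS) to covariate and blocked analyses. It does not say that they stay in the Aim 2 model.

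**The concern.** A hypothesis about one named exposure needs an adjusted estimate whose adjustment set was chosen without looking at the outcome. Here the exposure (called masking at this point in the text) is in a group that is subject to reduction, and so are the variables that confound it. Two things can then go wrong.

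1. A confounder that is real but too weak to survive selection in 120 people is removed. Its effect is credited to expressive capacity.
2. The p-value and interval from the final model are computed as if that model had been fixed in advance.

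The over-fitting check has no stated method, and tuning is a further data-dependent step. It does not repair either problem. Because Aim 3 reuses these models, the gender-moderation result inherits them.

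The role of access to support is also open. The term is undefined, and it overlaps the network and resource outcomes (primary outcomes 3 and 4 under Models for longitudinal trajectories). For those outcomes, adjusting for it could adjust away part of what is being modelled.

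**Working it through.** **1. The plan's own power figure.** Inputs from the Power Calculation section: n = 120, seven visits, ICC 0.82, 15% dropout a year, α = 0.05 (sidedness not stated), r = 0.23. Formula: power = Φ(atanh(r)·√(n−3) − z), with atanh(0.23) = 0.2342.

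- Two-sided, n = 120: Φ(0.2342 × 10.817 − 1.960) = Φ(0.573) = 71.7%
- One-sided, n = 120: Φ(2.533 − 1.645) = Φ(0.888) = 81.3%
- Two-sided, seven visits: f = (1 + 6 × 0.82)/7 = 0.846, effective n = 120/0.846 = 141.9, power 78.8%
- The same with dropout (mean 5.56 visits): f = 0.852, effective n = 140.8, power 78.5%

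The stated 80% is reproduced to within 2 points by the last three readings. None of them allows for model selection.

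**2. How much confounding is at stake.** The documents give no correlations, so two sets were assumed, in SD units. The shift in the exposure coefficient if every confounder were omitted is Σ(correlation with exposure × effect on outcome).

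- Set A (motor 0.5, GDS 0.3, MoCA −0.25; effects 0.20, 0.20, −0.15): 0.5×0.20 + 0.3×0.20 + 0.25×0.15 = 0.10 + 0.06 + 0.0375 = 0.1975
- Set B (eight covariates, each with correlation 0.2 and effect 0.12): 8 × 0.2 × 0.12 = 0.192

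Both are nearly as large as the effect the study is powered for. Selection removes part of the adjustment. In Set B with the exposure forced in, no true effect and elimination at p>0.05, the mean estimate was 0.125 instead of 0.

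**3. Simulation.** Person-level regression (for example, of a slope), N = 120, backward elimination by group at p>0.05 or p>0.157, 2,000 to 4,000 runs per setting where the count is recorded. Ranges reflect the threshold and how the elimination is programmed.

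| No true effect: type I error | Set A | Set B | No confounding (Set B layout, p>0.05) |
|---|---|---|---|
| Exposure can be dropped | 8–16% | 14–22% | 4.6% |
| Exposure forced in, confounders selected | 15–27% | 16–30% | 4.6% |
| Fixed set | about 5% | 4.6–5.7% | 4.7–4.8% |

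| True effect: coverage of the 95% CI | Set A (effect 0.20) | Set B (effect 0.25) |
|---|---|---|
| Exposure can be dropped, when kept | 57–84% | 67–84% |
| Exposure forced in, confounders selected | – | 69–83% |
| Fixed set | about 95% | 94–96% |

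Without confounding and with a true effect, coverage stayed at 93–97%.

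Forcing in the exposure alone is therefore not a cure: the type I error comes from the confounders that are removed.

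**The case against.** Several points on the other side stand.

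- **Order of entry.** A reader might infer that the exposure appears only at the end. It does not: baseline expressive capacity is named in the preliminary model. Entering an exposure after demographic and clinical factors is ordinary hierarchical adjustment and causes no bias by itself. But the preliminary step only guides what follows, and it is not designated as the Aim 2 test.
- **No significance rule is stated.** Reduction could rest on subject matter, collinearity or composites; the expressive behaviour scores are themselves composites from principal component analysis. That the exposure can be dropped follows from silence. The references to guiding, fit and fine-tuning point to a data-driven process but do not prove it. If the grounds are subject-matter ones, the retained list can be written down now.
- **Unconditional bias is not shown.** A reader might conclude that the Aim 2 estimate is invalid and biased whatever happens. Without confounding the distortion is small: with a droppable exposure and a true effect of 0.25, the mean when kept was 0.283 (0.283/0.25 = 1.13, or 13% too large), and with the exposure forced in it was 0.249.
- **Inflation among kept estimates misleads.** In Set A with a true effect of 0.20, masking was dropped in 34–40% of runs and averaged 0.31–0.37 when kept. Most of that is low power and ordinary significance filtering: the fixed model was non-significant in 63% of runs, and its significant estimates averaged 0.32. The type I error with the exposure forced in does not have this weakness.
- **Exploratory tone.** This is an observational cohort and parts of the plan speak of exploring. The trigger analysis is labelled exploratory; Aim 2 is not, and it carries a directional hypothesis.

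**Conclusion.** The point holds as a fault of pre-specification, and it should be fixed. The plan states a reduction rule that covers the exposure's group and protects neither the exposure nor the confounders it admits. It designates no primary Aim 2 model and offers no safeguard for inference after selection. If the reduction is data-driven, ordinary p-values and intervals are not valid in general. Under assumed moderate confounding, type I error was about 8–22% with a droppable exposure and 15–30% with the exposure forced in, against about 5% for a fixed set; without confounding it was near 5%.

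These sizes rest on assumed correlations, effects and thresholds, and on a person-level regression in place of the seven-visit mixed model. They also take masking and expressive capacity to be the same exposure; the plan uses the terms interchangeably without defining them. The documents do not support the stronger conclusion that the Aim 2 result is certain to be biased, or by how much.

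**What to change.** Name one primary Aim 2 model for each outcome:

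- Always retain time, baseline expressive capacity and their interaction.
- Always retain a fixed list of baseline confounders already collected, at least age, gender, GDS and MoCA, with no data-driven removal. Because the target is a slope, state whether these also enter with their time interactions.
- Decide in advance, outcome by outcome, whether access to support and the MDS-UPDRS motor score are adjusters. Do not adjust for a component of the outcome being modelled.
- Put motor score in a sensitivity model. It is primary outcome 10, and the Covariate measures section describes reduced expressivity as a motor problem, so adjusting for it may remove part of the exposure.
- Use one defined term for the exposure.
- Label the stepwise build-up, transformations and fine-tuning as exploratory, and carry the fixed model into Aim 3.

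The cost is wording and a little precision. With k covariates, √(n−3) becomes √(n−3−k). For a partial correlation of 0.23, two-sided, n = 120, power goes from 71.7% to Φ(0.2342×√113 − 1.960) = 70.2% with four covariates and Φ(0.2342×√109 − 1.960) = 68.6% with eight. At effective n = 140.8 it goes from 78.5% to about 77% and 76%. No new data are needed.
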